12. PROCEDURE FOR HANDLING PRODUCT QUALITY COMPLAINTS

A Product Quality Complaint (PQC) refers to any written, electronic, or oral communication that alleges deficiencies related to the identity, quality, durability, reliability, safety, effectiveness or performance of test articles after they have been released for clinical trial use.

Potential complaints may come from a variety of sources including but not limited to subjects, clinical research associates (CRA), clinical operations managers (COM), medical monitors, and site personnel, etc. The following are not considered product quality complaints:

- Subject satisfaction inquiries reported via "Subjective Questionnaires" and "Patient Reported Outcomes (PRO)."
- Clinical test articles that are stored improperly or damaged after receipt at the investigational site.
- Lens replacements that occur due to drops/fall-outs.
- Damage deemed by clinicians or clinical staff to be caused by handling by the user, and not indicative of a quality deficiency (i.e. tears, rips, etc.), only in situations where there is no deficiency alleged by the subject.

Within 24 hours of site personnel becoming aware that a PQC has occurred, the PQC must be recorded in the EDC system, which will trigger an automatic email notification to the appropriate COM/CRA and Clinical QA representative. In cases where the EDC system in use is not configured to send automatic notifications or when an EDC system is not used, the COM/CRA is responsible for notifying Clinical QA upon discovery that a PQC has occurred.

Upon receipt of the EDC notification, the COM/CRA will contact the study site to collect additional information which will include:

- Date the complaint was received/recorded in the EDC System (Date of Sponsor Awareness).

Clinical Study Protocol

Johnson & Johnson Vision Care, Inc.

- Who received the complaint.
- Study number.
- Clinical site information (contact name, site ID, telephone number).
- Lot number(s).
- Unique Subject Identifier(s).
- Indication of who first observed complaint (site personnel or subject).
- OD/OS indication, along with whether the lens was inserted.
- Any related AE number if applicable.
- Detailed complaint description (scheduled/unscheduled visit, wear time, symptoms, resolution of symptoms, etc.).
- Eye Care Provider objective (slit lamp) findings if applicable.
- Confirmation of product availability for return (and tracking information, if available), or rationale if product is not available for return [REDACTED]
[REDACTED]

Once a complaint is received, it will be assessed by the COM, CRA, or trained site personnel to determine if it is an Adverse Event/Serious Adverse Event (AE/SAE). If the complaint results in an AE/SAE, the COM/CRA, or trained site personnel will follow Section 13 of this protocol. If the AE/SAE was potentially the result of a product quality related deficiency, these procedures also apply and will be executed in parallel.

In some cases, a PQC form may be generated in EDC by the site in error. In this event, the PQC forms will be marked “Intentionally Left Blank” or “ILB”. Justification for ILB must be documented.

13. ADVERSE EVENTS

13.1. Definitions and Classifications

Adverse Event (AE) – An AE is “any untoward medical occurrence, unintended disease or injury, or untoward clinical signs (including abnormal laboratory findings) in subjects, users or other persons, whether or not related to the investigational medical device.”

Note: This definition includes events related to the investigational medical device or the comparator, and to the procedures involved. For users or other persons, this definition is restricted to events related to investigational medical devices.¹

An AE includes any condition (including a pre-existing condition) that:

1. Was not present prior to the study, but appeared or reappeared following initiation of the study.
2. Was present prior to the study but worsened during the study. This would include any condition resulting from concomitant illnesses, reactions to concomitant medications, or progression of disease states.

Note: Pregnancy must be documented as an adverse event and must be reported to the clinical monitor and to the Sponsor immediately upon learning of the event.

Serious Adverse Event (SAE) – An SAE is any adverse event that led to any of the following:

Clinical Study Protocol

Johnson & Johnson Vision Care, Inc.

- Death
- Serious deterioration in the health of the subject that resulted in any of the following:
- Life-threatening illness or injury
- Permanent or persistent impairment of a body structure or a body function
- Hospitalization or prolongation of patient hospitalization
- Medical or surgical intervention to prevent life-threatening illness or injury or permanent impairment to a body structure or a body function.
- Chronic disease
- Foetal distress, foetal death or a congenital physical or mental impairment of birth defect.

Diagnoses and conditions that are considered Ocular Serious Adverse Events include, but not limited to:

- Microbial Keratitis (MK)
- Iritis (including cells in the anterior chamber)
- Permanent decrease in best spectacle corrected visual acuity equivalent to 2 acuity lines or greater
- Central Corneal Opacity
- Central Corneal Neovascularization
- Uveitis
- Endophthalmitis
- Hypopyon
- Hyphemia
- Penetration of Bowman's Membrane
- Persistent Epithelial Defect
- Limbal cell Damage leading to Conjunctivalization

Significant Adverse Events – are defined as events that are symptomatic and warrant discontinuation (temporary or permanent) of the contact lens wear

Diagnoses and conditions that are considered Ocular Significant Adverse Events include, but not limited to the following:

- Contact Lens Induced Peripheral Ulcer (CLPU)
- Significant Infiltrative Events (SIE)
- Superior Epithelial Arcuate Lesions (SEALs)
- Any Temporary Loss of > 2 Lines of BSCVA
- Other grade 3 or higher corneal findings, such as abrasions or edema
- Non-contact lens related corneal events - e.g. Epidemic Keratoconjunctivitis (EKC)
- Asymptomatic Corneal Scar
- Any corneal event which necessitates temporary lens discontinuation > 2 weeks

Non-Significant Adverse Events – are defined as those events that are usually asymptomatic and usually do not warrant discontinuation of contact lens wear but may cause a reduction in

Clinical Study Protocol

Johnson & Johnson Vision Care, Inc.

wear time. However, the Investigator may choose to prescribe treatment as a precautionary measure.

Diagnoses and conditions that are considered Ocular Non-Significant Adverse Events include, but not limited to the following:

- Non-significant Infiltrative Event (NSIE)
- Contact Lens Papillary Conjunctivitis (CLPC)
- Superficial Punctate Keratitis (SPK)
- Conjunctivitis: Bacterial, Viral, Allergic
- Blepharitis
- Meibomianitis
- Contact Dermatitis
- Localized Allergic Reactions
- Any corneal event not explicitly defined as serious or significant adverse event, which necessitates temporary lens discontinuation < 2 weeks

Adverse Device Effect (ADE) – An ADE is an “adverse event related to the use of an investigational medical device.”

Note 1: This definition includes adverse events resulting from insufficient or inadequate instructions for use, deployment, implantation, installation, or operation, or any malfunction of the investigational medical device.

Note 2: This definition includes any event resulting from use error or from intentional misuse of the investigational medical device.¹

Unanticipated Adverse Device Effect (UADE) – A UADE is any serious adverse effect on health or safety or any life-threatening problem or death caused by, or associated with, the test article, if that effect, problem, or death was not previously identified in nature, severity, or degree of incidence in the investigational plan, Investigator’s Brochure or protocol, or any other unanticipated serious problem associated with the test article that relates to the rights, safety and welfare of subjects.

13.2. Assessing Adverse Events

In conjunction with the medical monitor, the Investigator will evaluate adverse events to ensure the events are categorized correctly. Elements of categorization will include:

- Seriousness/Classifications (see definition in section 13.1).
- Causality or Relatedness – i.e. the relationship between the test article, study treatment or study procedures and the adverse event (not related, unlikely related, possibly related, or related - see definition in section 13.2.1).
- Adverse Event Severity – Adverse event severity is used to assess the degree of intensity of the adverse event (mild, moderate, or severe - see definition in section 13.2).
- Outcome – not recovered or not resolved, recovering or resolving, recovered or resolved with sequelae, recovered or resolved, death related to adverse event, or unknown.

Clinical Study Protocol

Johnson & Johnson Vision Care, Inc.

- Actions Taken – none, temporarily discontinued, permanently discontinued, or other.

13.2.1. Causality Assessment

Causality Assessment – A determination of the relationship between an adverse event and the test article. The test article relationship for each adverse event should be determined by the investigator using these explanations:

- Not Related- An adverse event that is not related to the use of the test article, study treatment or study procedures.
- Unlikely Related – An adverse event for which an alternative explanation is more likely, e.g. concomitant treatment, concomitant disease(s), or the relationship of time suggests that a causal relationship is not likely.
- Possibly Related – An adverse event that might be due to the use of the test article, or to the study treatment or study procedures. An alternative explanation, e.g. concomitant treatment, concomitant disease(s), is inconclusive. The relationship in time is reasonable. Therefore, the causal relationship cannot be excluded.
- Related – An adverse event that is listed as a possible adverse effect (device) or adverse reaction (drug) and cannot be reasonably explained by an alternative explanation, e.g. concomitant treatment of concomitant disease(s). The relationship in time is very suggestive, e.g. it is confirmed by de-challenge and re-challenge.

13.2.2. Severity Assessment

Severity Assessment – A qualitative assessment of the degree of intensity of an adverse event as determined by the Investigator or reported to him/her by the subject. The assessment of severity is made irrespective of test article, study treatment or study procedure relationship or seriousness of the event and should be evaluated according to the following scale:

- Mild – Event is noticeable to the subject but is easily tolerated and does not interfere with the subject's daily activities.
- Moderate – Event is bothersome, possible requiring additional therapy, and may interfere with the subject's daily activities.
- Severe – Event is intolerable, necessitates additional therapy or alteration of therapy and interferes with the subject's daily activities.

13.3. Documentation and Follow-Up of Adverse Events

The recording and documenting of adverse events (ocular and non-ocular) begin when the subjects are exposed to the test article, study treatment or study procedure. Adverse events reported before the use of test article, start of study treatment, or study procedures will be recorded as medical history. However, if the condition deteriorates at any time during the study it will be recorded and reported as an AE. Untoward medical events reported after the subject's exit from the study will be recorded as adverse events at the discretion of the Investigator.

Upon finding an adverse event, the Principal Investigator will document the condition in the subject record and in the eCRFs and complete the Adverse Event eCRF.

Clinical Study Protocol **Johnson & Johnson Vision Care, Inc.**

Complete descriptions of all adverse events must be available in the subject record. All Adverse Events including local and systemic reactions not meeting the criteria for “serious adverse events” shall be captured on the appropriate case report form or electronic data system. All adverse events occurring while the subject is enrolled in the study must be documented appropriately regardless of relationship.

It is the Investigator’s responsibility to maintain documentation of each reported adverse event. All adverse events will be followed in accordance with applicable licensing requirements. Such documentation will include the following:

- Adverse event (diagnosis not symptom).
- Drawings or photographs (where appropriate) that detail the finding (e.g., size, location, and depth, etc.).
- Date the clinical site was notified.
- Date and time of onset.
- Date and time of resolution.
- Adverse event classification, severity, and relationship to test articles, as applicable.
- Treatment regimen instituted (where appropriate), including concomitant medications prescribed, in accordance with applicable licensing requirements.
- Any referral to another health care provider if needed.
- Outcome, ocular damage (if any).
- Likely etiology.
- Best corrected visual acuity at the discovery of the event and upon conclusion of the event, if the AE is related to the visual system.

Upon discovery of an AE that is deemed ‘possibly related’ or ‘related’ to the test article or study procedures (whether related to the visual system or not), an AE review form [REDACTED] must be completed. Additional dated and initialed entries should be made at follow-up evaluations. Separate forms must be completed for each eye if the AE is bilateral.

In addition, if an infiltrate(s) is present, he/she will complete the Corneal Infiltrate Assessment eCRF. Where necessary, a culture of the corneal lesion will be collected to determine if the infection is microbial in nature. If cultures are collected, the date of culture collection and laboratory utilized will be recorded.

Changes in the severity of an AE shall be documented to allow an assessment of the duration of the event at each level of intensity to be performed. Adverse events characterized as intermittent require documentation of the onset and duration of each episode. Changes in the assessment of relationship to the Test Article shall also be clearly documented.

Subjects who present with an adverse event shall be followed by the Investigator, within licensure, until all signs and symptoms have returned to pre-treatment status, stabilized, or been satisfactorily resolved. If further treatment beyond licensure is required, the patient will be referred to the appropriate health care provider. The Investigator will use his/her clinical judgment as to whether a subject reporting with an adverse event will continue in the study. If a subject is discontinued from the study, it will be the responsibility of the Investigator to

Clinical Study Protocol

Johnson & Johnson Vision Care, Inc.

record the reason for discontinuation. The Investigator will also document the adverse event appropriately and complete the Adverse Event eCRF. Any subjects with ongoing adverse events related to the test article, study treatment or study procedures, as of the final study visit date, should be followed to resolution of the adverse event or until referral to an appropriate health care provider, as recommended by the Investigator. Non-ocular adverse events that are not related to the test article, study treatment, or study procedures may be recorded as “ongoing” without further follow-up.

13.4. Reporting Adverse Events

The Investigator will notify the Sponsor of an adverse event by e-mail, facsimile, or telephone as soon as possible and no later than 24 hours from discovery for any serious /significant adverse events, and 2 days from discovery for any non-significant adverse event. In addition, a written report will be submitted by the Principal Investigator to the IEC/IRB according to their requirements (section 13.4.2). The report will comment whether the adverse event was considered to be related to the test article, study treatment or study procedures.

13.4.1. Reporting Adverse Events to Sponsor

Serious/Significant Adverse Events

The Investigator will inform the sponsor of all serious/significant adverse events occurring during the study period as soon as possible by e-mail or telephone, but no later than 24 hours following discovery of the event. The Investigator is obligated to pursue and obtain information requested by the Sponsor in addition to that information reported on the eCRF. All subjects experiencing a serious/significant adverse event must be followed up and all outcomes must be reported.

When medically necessary, the Investigator may break the randomization code to determine the identity of the treatment that the subject received. The Sponsor and study monitor should be notified prior to unmasking the test articles.

In the event of a serious/significant adverse event, the Investigator must:

- Notify the Sponsor immediately.
- Obtain and maintain in the subject’s records all pertinent medical information and medical judgment for colleagues who assisted in the treatment and follow-up of the subject.
- Provide the Sponsor with a complete case history which includes a statement as to whether the event was or was not related to the use of the test article.
- Notify the IEC/IRB as required by the IEC/IRB reporting procedure according to national regulations.

Unanticipated (Serious) Adverse Device Effect (UADE)

In the event of an Unanticipated (Serious) Adverse Device Effect (UADE), the Investigator will submit a report of the UADE to the Sponsor and IEC/IRB as soon as possible, but no later than 24 hours after the Investigator first learns of the effect. This report is in addition to the immediate notification mentioned above.

Clinical Study Protocol

Johnson & Johnson Vision Care, Inc.

The Sponsor must conduct an evaluation of the UADE and must report the results of the evaluation to FDA, the IEC/IRB and participating Investigators within 10 working days after the Sponsor first receives notification of the effect.

Non-Serious Adverse Events

All non-serious adverse events, including non-serious adverse device effects, will be reported to the sponsor by the Investigator no later than 2 days from discovery.

13.4.2. Reporting Adverse Events to the Responsible IEC/IRB and Health Authorities

Adverse events that meet the IEC/IRB requirements for reporting must be reported within the IEC/IRB's written guidelines. Each clinical site will refer to and follow any guidelines set forth by their Approving IEC/IRB. Each clinical site will refer to and follow any guidelines set forth by their local governing Health Authorities.

The Sponsor will report applicable Adverse Events to the local health authorities according to the written guidelines, including reporting timelines.

13.5. Event of Special Interest

None

13.6. Reporting of Pregnancy

Subjects reporting pregnancy (by self-report) during the study will be discontinued after the event is recorded as an Adverse Event. Once discontinued, pregnant participants and their fetuses will not be monitored for study related purposes. Pregnant participants are not discontinued from contact lens or solution related studies for safety concerns, but due to general concerns relating to pregnancy and contact lens use. Specifically, pregnant women are discontinued due to fluctuations in refractive error and/or visual acuity that occur secondary to systemic hormonal changes, and not due to unforeseen health risks to the mother or fetus.

14. STATISTICAL METHODS

14.1. General Considerations

Statistical Analysis will be undertaken by the sponsor or under the authority of the sponsor. A general description of the statistical methods to be implemented in this clinical trial is outlined below.

All data summaries and statistical analyses will be performed using the Statistical Analysis System (SAS) software Version 9.4 or higher (SAS Institute, Cary, NC). Throughout the analysis of data, the results for each subject/eye will be used when available for summarization and statistical analysis. Unscheduled visits will be summarized separately and will be excluded from the statistical analysis.

Summary tables (descriptive statistics and/or frequency tables) will be provided for all baseline variables, efficacy variables and safety variables as appropriate. Continuous variables will be

Clinical Study Protocol

Johnson & Johnson Vision Care, Inc.

summarized with descriptive statistics (n, mean, standard deviation [SD], median, minimum and maximum). Frequency count and percentage of subjects or eyes within each category will be provided for categorical data.

14.2. Sample Size Justification

This is a pilot study assessing the clinical performance of a marketed contact lens Bausch + Lomb Ultra® Multifocal for Astigmatism with respect to objective vision. This is the first time the sponsor will be assessing this study lens; therefore, historical data is not available to perform any statistical power calculation. The sample size was chosen by the study responsible clinician and was determined based on previous studies on other multifocal toric contact lenses with similar study endpoints.

14.3. Analysis Populations

Safety Population:

All subjects who were administered any test article excluding subjects who drop out prior to administering any test article. At least one observation should be recorded.

Per-Protocol Population:

All subjects who have successfully completed all visits and did not substantially deviate from the protocol as determined by the trial cohort review committee prior to database hard lock (Per-Protocol Population). Justification of excluding subjects with protocol deviations in the Per-Protocol Population set will be documented in a memo to file.

Intent-to-Treat (ITT) Population:

All randomized subjects regardless of actual treatment and subsequent withdrawal from study or deviation from protocol. At least one observation should be recorded.

14.4. Level of Statistical Significance

All planned analysis for this study will be conducted with an overall type I error rate of 5%.

14.5. Primary Analysis

LogMAR Visual Acuity

Binocular, high luminance, high contrast visual performance on logMAR scale will be analyzed using a linear mixed model. Each model will include the experimental design factors: distance (distance/intermediate/near) as fixed effect. Site will be included as random covariate when appropriate. Other baseline characteristics known of importance such as age, gender and/or add power will be included as fixed covariates when appropriate. The covariance between residual errors from the same subject across different distances will be selected based on the finite-sample corrected Akaike's Information Criterion (Keselman et al. 1998).⁸ Covariance structures considered may include: Homogenous compound symmetry (CS) and Unstructured covariance structure (UN). The structure that returns the lowest Akaike Information Criteria Corrected (AICC) will be selected as the structure that best fit the data.

Clinical Study Protocol

Johnson & Johnson Vision Care, Inc.

The Kenward and Roger method will be used for the calculation of the denominator of degrees of freedom.⁹

Comparisons will be carried out using 95% confidence intervals constructed of least-square means (LSM) from the linear mixed models. Statistically superiority will be concluded if the upper limits of the confidence intervals are below the thresholds for corresponding distances.

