Johnson & Johnson Vision Care, Inc.

SYNOPSIS

Protocol Title	Evaluation of Visual Acuity with a Reusable Toric Multifocal Contact Lens
Sponsor	JJVC, [name]
Clinical Phase	Clinical trial phase: Post-market Design control phase: Not applicable.
Trial Registration	This study will be registered on ClinicalTrials.gov based on the following: The clinical trial is evaluating a U.S. FDA-regulated Device Product
Test Article	Marketed Product: Bausch + Lomb Ultra® Multifocal for Astigmatism contact lens manufactured in samfilcon A material.
Wear and Replacement Schedules	Wear Schedule: The lenses will be used on a daily reusable basis for approximately five weeks (1 week trial followed by 4 week dispense of optimized pair). Replacement Schedule: The lenses will be replaced at the first follow-up visit only.
Objectives	Primary Objective The primary objective of this study is an evaluation of the logMAR visual performance with the study lenses after 4 weeks of wear. Secondary Objective Not applicable. Exploratory Objective Not applicable.
Study Endpoints	Primary endpoints: logMAR visual acuity at distance (4 M), intermediate (64 cm) and near (40 cm).
Study Design	The study is a bilateral, single-masked, single-arm, 4-visit dispensing study. There will be one study treatment, with the subject being in the treatment for approximately five weeks. Approximately 90 eligible subjects will be enrolled, with the aim to complete at least 80 subjects. The subjects will be fit in the study lens and wear the study lenses for 5-9 days then undergo optimization and wear the optimized pair for 4 weeks (25-31 days), with an interim follow-up visit at 2 weeks (12-16 days). The primary endpoint will be logMAR visual performance. See the flow chart at the end of the synopsis table for the schematic of the study visits and procedures of main observations (Figure 1).

Clinical Study Protocol
Johnson & Johnson Vision Care, Inc.

Sample Size	Approximately 50 myopic subjects with against-the-rule astigmatism will be enrolled, with the aim that at least 45 will complete the study. Approximately 40 hyperopic subjects with against-the-rule astigmatism will be enrolled, with the aim that at least 35 will complete the study.
Study Duration	The study will last approximately 2-3 months.

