Anticipated Study Population	Healthy male and female volunteers with presbyopia, astigmatism and either myopia or hyperopia will be screened as per criteria outlined below. All volunteers will have baseline measurements taken to ensure eligibility. The baseline procedures will occur after informed consent has been obtained. For a detailed list of procedures see the time and events schedule listed below.
Eligibility Criteria	
Potential subjects must satisfy all of the following criteria to be enrolled in the study:
 
Inclusion Criteria following Screening The subject must:
 
 1. Read, understand, and sign the STATEMENT OF INFORMED CONSENT and receive a fully executed copy of the form. 2. Appear able and willing to adhere to the instructions set forth in this clinical protocol. 3. Be at least 40 and not more than 70 years of age at the time of screening. 4. Own a wearable pair of spectacles if required for their distance vision. 5. Be an adapted soft contact lens wearer in both eyes (i.e. has worn lenses a minimum of 2 days per week for at least 8 hours per wear day, for the past month). 6. Be an existing wearer of a presbyopic contact lens correction (e.g., reading spectacles over contact lenses, multifocal or monovision contact lenses, etc.) or respond positively to at least one symptom on the “Presbyopic Symptoms Questionnaire”. 
Inclusion Criteria at Baseline The subject must:
 
 7. Have distance spherical component of refraction in the range of either -1.25 D to -3.75 D or +1.25 to +3.75 D in each eye.

Clinical Study Protocol

Johnson & Johnson Vision Care, Inc.

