2.3. Hypotheses

Primary Hypotheses

1. After 25-31 days of wear, the binocular, high-luminance, high-contrast distance (4 M) logMAR visual acuity of the test lens will be statistically better than 0.00 logMAR. This will be determined using ETDRS LogMAR acuity testing charts.
2. After 25-31 days of wear, the binocular, high-luminance, high-contrast intermediate (64 cm) logMAR visual acuity of the test lens will be statistically better than +0.17 logMAR. This will be determined using Guillon/Poling LogMAR acuity testing charts.
3. After 25-31 days of wear, the binocular, high-luminance, high-contrast near (40 cm) logMAR visual acuity of the test lens will be statistically better than +0.17 logMAR. This will be determined using Guillon/Poling LogMAR acuity testing charts.

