3. TARGETED STUDY POPULATION

3.1. General Characteristics

The population to be studied will consist of adapted contact lens wearers who have astigmatism in both eyes. Approximately 90 eligible subjects (50 myopes with against-the-rule astigmatism and 40 hyperopes with against-the-rule astigmatism) will be enrolled with at least 80 targeted to complete. Subjects to be enrolled will have -0.75 D to -1.75 D of astigmatism in both eyes with $90^\circ \pm 25^\circ$ axis.

Clinical Study Protocol

Johnson & Johnson Vision Care, Inc.

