4.3. Enrollment Target and Study Duration

Approximately 50 eligible myopes with against-the-rule astigmatism and 40 eligible hyperopes with against-the-rule astigmatism will be enrolled with at least 80 targeted to complete. The study will last approximately 2-3 months.

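### Refractive group, the only factor with its own enrolment targets, is not pre-specified in the primary model, and no by-group acuity result is planned

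*Combined protocol and SAP*

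**What the plan says.** The Synopsis (Sample Size) sets separate targets: "Approximately 50 myopic subjects with against-the-rule astigmatism will be enrolled, with the aim that at least 45 will complete the study" and "Approximately 40 hyperopic subjects with against-the-rule astigmatism will be enrolled, with the aim that at least 35 will complete the study". Section 3.1 repeats the enrolment split ("50 myopes with against-the-rule astigmatism and 40 hyperopes with against-the-rule astigmatism"), as does Section 4.3. No other characteristic has its own target.

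Section 14.5 specifies a linear mixed model for binocular, high-luminance, high-contrast logMAR acuity: "Each model will include the experimental design factors: distance (distance/intermediate/near) as fixed effect". Site may enter as a random term. Other baseline characteristics may enter where judged appropriate, with age, gender and add power given as examples. Refractive group is not among the examples. Success at each distance requires the upper limit of the 95% confidence interval for the least-squares mean to lie below that distance's threshold.

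The hypotheses in Section 2.3 are pooled over refractive groups; at near, for example, "high-contrast near (40 cm) logMAR visual acuity of the test lens will be statistically better than +0.17 logMAR". Sections 14.6 and 14.7 are marked as not applicable. Section 14.1 promises summaries as appropriate, without naming a split. Section 4.2 plans aggregate comparisons with two earlier studies and also names no split.

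**The concern.** A factor used to control recruitment would normally be carried into the analysis. Here it is fixed at the design stage and then left to later choice: the open covariate clause permits a group term and Section 14.1 permits a split table, but neither commits to one.

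Two consequences are possible, and both depend on how far the groups differ.

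1. **Precision.** The pooled interval carries between-group variance that a group term would remove.
2. **Masking.** A pooled pass at a distance could coexist with one refractive group at or above the threshold, with no planned output to reveal it.

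The second matters more, because readers may take a pooled pass as describing both kinds of wearer.

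**Working it through.** **Inputs from the documents.** Completers: 45 myopes and 35 hyperopes, 45 + 35 = 80, which agrees with the stated total. Near threshold: +0.17 logMAR (Section 2.3). Pass: upper 95% limit below the threshold (Section 14.5), read here as two-sided. There is no power figure to reproduce; Section 14.2 says "therefore, historical data is not available to perform any statistical power calculation".

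**Assumptions.** Within-group SD *s* of 0.08 or 0.10, equal in both groups; gap *d* between group means of 0 to 0.08; one distance at a time; complete data; no site or other covariates. The documents give neither *s* nor *d*.

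**Interval width.**

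- Without group: half-width = t(79) × √{[s² + (45×35/80)·d²/79]/80}
- With group, weighted by observed sizes: half-width = t(78) × s/√80

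With s = 0.08 and d = 0.08:

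- 45×35/80 = 19.69, and 19.69/79 = 0.249.
- Without group: 1.990 × √(0.0064 × 1.249/80) = 0.0199.
- With group: 1.991 × 0.08/8.944 = 0.0178.
- The interval without group is about 12% wider.

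**Masking.** Put hyperopes at a true 0.18 and myopes better by *d*. The pooled mean is 0.18 − (45/80)·d, so at d = 0.08 it is 0.18 − 0.045 = 0.135. The expected upper limit is 0.135 + 0.0199 = 0.155, below 0.17, although hyperopes do not meet the threshold.

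Simulated results, 100,000 runs per case (pairs are SD 0.08 / 0.10):

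| Gap | Pooled pass, hyperopes at 0.18 | Same, group in model | Pooled pass, myopes at 0.18 | CI widening without group |
|---|---|---|---|---|
| 0.08 | 95.1 / 83.7% | 97.1 / 87.2% | 71.5 / 53.8% | 11.8 / 7.7% |
| 0.06 | 70.3 / 52.3% | 74.6 / 55.7% | 38.2 / 27.3% | 6.8 / 4.4% |
| 0.04 | 26.0 / 18.5% | 28.0 / 19.6% | 11.8 / 8.9% | 3.1 / 2.0% |
| 0.02 | 3.3 / 3.1% | 3.4 / 3.2% | 1.7 / 1.9% | 0.8 / 0.5% |

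With both groups at 0.18 (gap 0) the pooled test passes in 0.2% or less. A pooled pass becomes more likely than not at a gap of 0.051 / 0.059 with hyperopes worse, or 0.067 / 0.077 with myopes worse.

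If hyperopes sit exactly at 0.17 instead, smaller gaps suffice: the pooled test passes in 23 / 16% at a gap of 0.02, 68 / 50% at 0.04 and 95 / 83% at 0.06.

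**Error rate.** With the true pooled mean exactly 0.17, the one-sided error (nominal 2.5%) without group is 1.5 / 1.8% at a gap of 0.08, 2.2 / 2.3% at 0.04 and 2.5 / 2.4% at 0. With group and observed-size weights it is 2.4-2.6% throughout. Omitting group is therefore conservative and does not inflate the error rate.

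**The case against.** The strongest reply is that nothing in the plan is wrong. The hypotheses concern the lens overall, the pooled model tests them, and omitting group errs on the safe side. Viewing distance is the within-subject factor that defines the three hypotheses, while myopia or hyperopia is a baseline characteristic that the open covariate clause can admit. The targets are approximate, the study is a pilot of a marketed lens, and no document suggests a gap as large as 0.05-0.08. All of this stands, and it limits the point to pre-specification.

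A second objection is that adding group to the model makes a masked pass more likely, because the interval narrows: at SD 0.08 and a gap of 0.06 with hyperopes worse, the pass rate rises from 70.3% to 74.6%; with myopes worse, from about 38% to 43%. This is also correct. The group term recovers precision and restores the nominal error rate of the pooled test; only the by-group rows deal with masking.

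A third is that Section 4.2 already plans a comparison with earlier studies, one of which, by its title in the reference list, was in hyperopes. That section commits to no split by refractive group, so it does not fill the gap. It does strengthen the case for one, since the like-for-like figure for that comparison is the hyperope mean and not a mean over 56% myopes (45/80) and 44% hyperopes (35/80).

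Finally, inclusion criterion 7 is worded per eye and could be read to admit one eye of each sign. The plan already needs a rule to count subjects against its targets, and the same rule can serve the analysis, but it should be written down.

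**Conclusion.** The concern holds. Refractive group and by-group acuity are left to post-hoc choice, although group is the one factor the design controls by target. This is a worthwhile improvement and does not invalidate the primary test.

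The size depends on an unknown gap. At 0.02 logMAR the effect is negligible unless one group lies almost at the threshold. At 0.04 the precision loss is 2-3%, and a group truly at 0.18 usually makes the pooled near test fail. At 0.06-0.08 the loss is 4-12%, and with hyperopes at 0.18 the pooled test passes in 52-95% of trials. These figures rest on the assumed SD of 0.08-0.10, 45/35 completers and the single-distance simplification. They show what is possible, not what is likely.

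**What to change.** In Section 14.5:

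- Add refractive group (myope or hyperope, as counted toward the enrolment targets) and group-by-distance as fixed effects, and state how a subject is assigned to a group.
- Keep the overall least-squares mean at each distance as the primary test, and state that it is weighted by observed group sizes. Equal weights would move the estimate by (45/80 − 1/2)·d = 0.0625·d, which is 0.005 logMAR at a gap of 0.08.
- Report the mean and 95% interval by group at each distance as supportive estimates with no pass/fail claim, so the 5% error rate in Section 14.4 is unaffected.

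If the sponsor prefers to leave the primary model unchanged, pre-specified by-group mean and interval rows alone would close the reporting gap but not recover the precision.

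The cost is protocol wording, three more model parameters (one for group, two for the interaction) and a few table rows. Refraction is already recorded at Visit 1.

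The by-group rows have limits that should be stated with them. Half-widths are 0.024 / 0.030 for myopes and 0.027 / 0.034 for hyperopes, against 0.018 / 0.022 overall (SD 0.08 / 0.10). The between-group difference has half-width 0.036 / 0.045, so small differences stay unresolved. With both groups truly at 0.13, the hyperope upper limit still misses 0.17 in 17-35% of trials through smaller numbers alone, so these rows must not be read as tests.
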